9.3.6.5. Current Treatment

Medications assessed between the cohort entry date and end of follow-up (as defined in Section 9.2.5) will be included in descriptive analyses only and will not be included in the propensity score models. The medications include:

- Tofacitinib treatment;
 - Dose;
 - Treatment duration;
- TNF inhibitor treatment (eg, etanercept, adalimumab, golimumab, infliximab, certolizumab);
- Non-TNF biologics (eg, abatacept, rituximab, tocilizumab, sarilumab, anakinra, ustekinumab, vedolizumab);
- csDMARD treatment (eg, methotrexate, sulfasalazine, hydroxychloroquine, leflunomide, azathioprine);
- Immunosuppressants (eg, azathioprine, 6-mercaptopurine, cyclosporine);
- Other JAK inhibitor treatment (eg, baricitinib, upadacitinib);
- Corticosteroid treatment;
 - Average daily dose (eg, None, ≤ 5 mg/day, >5 to ≤ 10 mg/day, >10 to ≤ 20 mg/day, and >20 mg/day of prednisone average dose equivalent);
- 5-aminosalicylates (eg, mesalamine, balsalazide, olsalazine);
- Ozanimod.

Additional therapies that are approved for the treatment of UC or RA may be incorporated if they become available.

9.4. Data Sources

The patients included in this study will be drawn from the ORD and the Optum MA-PD, each as described below. The use of 2 databases is necessary to enable the findings from this study to be generalized to adults aged 18 years and older. The ORD will provide data on

adults under 65 years of age and MA-PD will provide data on adults 65 years of age and older (the ORD also includes some adults age 65+ years). The same patient does not appear in the 2 data sources simultaneously and the MA-PD operates similarly to the ORD, allowing us to easily pool the data for analysis.

As indicated in Section 9.2.3.2, RZV exposed patients will be matched to RZV unexposed patients from the same data source.

9.4.1. Optum Research Database

The ORD is a proprietary research database that contains the eligibility data, medical claims, and pharmacy claims from a large, commercial health plan affiliated with Optum. The individuals covered by this health plan are geographically diverse across the United States and comprise approximately 3% to 4% of the US population. As early as 1993, medical and pharmacy claims data are available for 65 million individuals with both medical and pharmacy benefit coverage. For 2021, data are available for approximately 12.6 million individuals with medical and pharmacy coverage.

Optum research activities utilize de-identified data from the ORD. Patient-identifiable information can only be accessed following approval of the study protocol by an appropriate institutional review board and privacy board. All data access conforms to applicable Health Insurance Portability and Accountability Act policies.

Accessible information from the ORD includes demographics, pharmacy use, and all medical and facility claims, which provide data on services, procedures, and their accompanying diagnoses.

The coding of medical claims conforms to insurance industry standards including:

- Use of designated claims forms (eg, physicians use the Health Care Financing Agency-1500 format and hospitals use the UB-04 or UB-92 format);
- International Classification of Diseases, 9th Revision codes;
- ICD-10 codes;
- CPT[®] codes³;
- HCPCS codes;
- Cost information;
- De-identified patient and provider codes.

³ CPT copyright 2022 American Medical Association. All rights reserved.

Claims for pharmacy services are typically submitted electronically by the pharmacy at the time prescriptions are filled. Pharmacy claims data allowing for longitudinal tracking of medication refill patterns and changes in medications include:

- NDC;
- Drug name;
- Dosage form;
- Drug strength;
- Fill date;
- Days of supply;
- Cost information;
- De-identified patient and prescriber codes.

An important advantage of the ORD is the large number of patients that can be studied because the data are routinely collected and maintained in computerized data files. The completeness of the data allows investigators to link any number of patient, physician, and treatment attributes, while maintaining the de-identified nature of the data. The database also captures a longitudinal record of medical services, irrespective of treatment site.

9.4.2. Optum Medicare Advantage and Medicare Part D Data

Beginning in 2006, complete medical and pharmacy information is available for Medicare enrollees with medical and Medicare Part D coverage. The pharmacy claims contain sufficient information to trace patients' pharmacy expenditures through the multiple phases of the Medicare Part D plans. For 2021, data are available for approximately 7.0 million individuals with both medical and pharmacy benefit coverage. Underlying information is geographically diverse across the country and fairly representative of the US Medicare population. Optum research activities utilize de-identified data from MA-PD. In limited instances, patient identifiers may be accessed where applicable law allows the use of patient-identifiable data, and when the study obtains appropriate approvals for accessing data that are not de-identified.

9.4.3. Supplemental Data Sources

9.4.3.1. Sociodemographic Data

Optum has a unique source of individual-level data, which is linked to the administrative claims data that allows for analysis of socioeconomic characteristics. The data populating these socioeconomic elements are generated by a combination of self-report, modeling, census data, classification based on surname and/or geography, and a variety of other

individual-level and population-level data sources. From this source of sociodemographic data, Optum will include race/ethnicity as a covariate for this study.

9.5. Study Size

[figure not shown]
Table 1 displays the counts of patients with RA and UC, and with RZV and tofacitinib exposure, that were observed in the ORD and MA-PD between October 2017 and December 2022. This count is for informational purposes only. Final sample size for the study could change depending upon criteria applied during the conduct of the protocol and required approvals.

Table 1. Counts of Tofacitinib and RZV Recipients Among Adults (18+) with RA or UC: ORD and MA-PD October 2017 to December 2022

Patient Characteristics	N
Patients with RA	446,618
Patients with UC	202,619
Patients with RA and/or UC	639,868
With a dispensing of tofacitinib	12,491
With receipt of RZV	100,005
With a dispensing of tofacitinib and receipt of at least one dose of RZV	2,744
With a dispensing of tofacitinib and receipt of two doses of RZV	1,932

Of the 2,744 tofacitinib users with RA or UC who received at least one dose of RZV, there were 1,932 (70%) who received two doses of RZV. These patients had a median of 11 tofacitinib dispensings, suggesting that there may be a subset of patients with tofacitinib exposure that overlaps both RZV doses. Assuming a background rate of HZ of 1.2 cases per 100 person-years among non-tofacitinib exposed patients with UC and RA²⁵ and an effectiveness of RZV in preventing HZ of 85%²⁶ among non-tofacitinib exposed patients with RA or UC, the sample size necessary to exclude 85% from the 95% confidence interval for the RZV effectiveness estimate for tofacitinib exposed patients with RA or UC was calculated. Figure 6 displays the upper bound of the 95% confidence interval for a range of estimated vaccine effectiveness and population sizes. Thus, for 2,000 RZV-exposed person-years, the upper 95% confidence interval bound of vaccine effectiveness would exclude 85% if the point estimate among tofacitinib exposed patients with RA or UC were 66.7% or lower (corresponding to an effect size of 21.5%, meaning that tofacitinib reduces the RZV effectiveness by 21.5%). For 4,000 RZV-exposed person-years, the estimated 95% confidence interval would exclude 85% if the point estimate among tofacitinib exposed patients with RA or UC were 70.8% or lower (corresponding to an effect size of 16.7%, meaning that tofacitinib reduces the RZV effectiveness by 16.7%). These estimates are generated for a range of plausible population sizes based on Optum feasibility counts shown in Table 1.

Figure 6. Upper Bound of Vaccine Effectiveness for a Range of Population Sizes and Vaccine Effectiveness Estimates

Assumptions: 1.2% HZ rate in unexposed; 2:1 matching of comparators to RZV exposed patients²⁷

Table 2. Prevalence of Zostavax Vaccination and Duration of Enrollment Among Adults (18+) with RA or UC Treated with Tofacitinib and Shingrix: Optum Claims Database, October 2017 to July 2022

	Patients with Tofacitinib and Shingrix	
	Patients <60 years of age N (%)	Patients ≥60 years of age N (%)
Total patients	649 (100.0%)	1,248 (100.0%)
Patients with a claim for Zostavax^a	16 (2.5%)	94 (7.5%)
With at least 1 year of enrollment prior to Shingrix ^a	544 (83.8%)	1,069 (85.7%)
Patients with a claim for Zostavax^b	16 (2.9%)	87 (8.1%)
With at least 2 years of enrollment prior to Shingrix ^a	437 (67.3%)	859 (68.8%)
Patients with a claim for Zostavax^b	15 (3.4%)	83 (9.7%)
With at least 3 years of enrollment prior to Shingrix ^a	340 (52.4%)	667 (53.5%)
Patients with a claim for Zostavax^b	13 (3.8%)	74 (11.1%)
With at least 4 years of enrollment prior to Shingrix ^a	264 (40.7%)	519 (41.6%)
Patients with a claim for Zostavax^b	10 (3.8%)	68 (13.1%)
With at least 5 years of enrollment prior to Shingrix ^a	205 (31.6%)	388 (31.1%)
Patients with a claim for Zostavax^b	7 (3.4%)	52 (13.4%)

^a Denominator for percent is the number of patients in the relevant age category (<60, ≥60).

^b Denominator for percent is the number of patients with the duration of enrollment (eg, 1, 2, etc) in the row above.

The prevalence of prior Zostavax vaccination and duration of enrollment among UC and RA patients treated with tofacitinib and Shingrix is shown in [Table 2](#). Among patients under age 60 years, 2.5% had prior exposure to Zostavax whereas 7.5% of patients 60 years of age and older had Zostavax exposure. Regarding duration of enrollment prior to receipt of Shingrix, over 80% of patients in both age groups had at least 1 year, while slightly more than 30% had at least 5 years of enrollment.

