Up to 2 comparators for each RZV initiator will be selected, matched on data source (ie, the Optum Research Database [ORD] or the Optum Medicare Advantage and Medicare Part D [MA-PD] Database) and other factors considered upon feasibility. Patients will be sampled with replacement. This process will be repeated for each 4-week window during the study period; as such, it is possible that a patient could be sampled as a comparator multiple times during the study. If patients are selected more than once into the study, it will be accounted for in the statistical analysis (Section 9.7.3).

Figure 4. Example of Time-Matched Vaccination Risk Sets in the RZV 2-Dose Analysis

If a patient selected for the comparator cohort subsequently receives RZV, their follow-up time within the comparator cohort will be censored upon the date of first administration of RZV. The patient may then be included in the RZV cohorts if they still meet all eligibility criteria. Consequently, patients are eligible to contribute person-time to the RZV cohort, the comparator cohort, or both the comparator cohort and (if subsequently vaccinated) the RZV cohort. Once a person contributes person-time to the RZV cohort, they are no longer eligible to contribute to the comparator cohort.

Patients with and without RZV exposure will be included in the UC RZV cohort and UC Comparator cohort, respectively, if they have at least one medical claim with a diagnosis of UC (International Classification of Diseases, 10th revision [ICD-10] code: K51*) in any position in the 365 days prior to and including their cohort entry date. Similarly, patients with and without RZV exposure will be included in the RA RZV cohort and RA Comparator cohort, respectively, if they have at least one medical claim with a diagnosis of RA (ICD-10 code: M05*) in any position in the 365 days prior to and including their cohort entry date. In addition, M06* (other rheumatoid arthritis) will also be used, except M06.1 (adult-onset Still’s disease) and M06.4 (inflammatory polyarthropathy). If a patient has claims with both UC and RA diagnoses in the 365 days prior to cohort entry, the claim closest to the cohort entry date will be used for cohort assignment.

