9.7.3.1. RZV 2-Dose Analysis

The RZV 2-dose analysis will be used as the main analysis for assessment of the primary objective for effectiveness. Incidence rates and corresponding 95% confidence intervals for the primary outcome (HZ) will be calculated before and after weighting. All analyses will be performed separately within the UC and RA cohorts. The incidence rate of HZ in the RZV 2-Dose cohort will be compared to the Comparator 2-Dose cohort. Weighted Kaplan-Meier plots will be used to depict the cumulative probability of survival (non-occurrence of the event).

Given the sampling approach that will be utilized in this study (sampling with replacement), we will calculate the number of patients that were selected and included in a study cohort more than once (Section 9.2.3.2.1). If that number exceeds 10% of the study population, then covariance between observations will be taken into account using an appropriate method (eg, generalised estimating equations or robust variance estimators).

The relative hazard will be calculated through weighted Cox regression models with appropriate 95% confidence intervals. Known confounders that are strongly associated with RZV receipt and HZ may also be included in the regression models as well as any variables with an absolute SD >0.1 between weighted exposure cohorts. Additional details on model selection will be detailed in the SAP.

Patients will be further stratified by the following patient groups relative to their matched comparators:

1. Tofacitinib current users at time of receipt of first and second RZV doses;
2. Tofacitinib current users at time of receipt of second RZV dose only.

The first subgroup analysis conducted among patients who receive two doses of RZV and are current users of tofacitinib at the time of receipt of both doses will be the main comparison.

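### Section 9.5 states precision for RA and UC combined, but every analysis is run separately by disease, so the stated thresholds, read as pooled totals, describe no planned estimate

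*Protocol*

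**What the plan says.** Section 9.5 of the protocol aims to "exclude 85% from the 95% confidence interval for the RZV effectiveness estimate for tofacitinib exposed patients with RA or UC". Its inputs are a comparator rate ("Assuming a background rate of HZ of 1.2 cases per 100 person-years among non-tofacitinib exposed patients with UC and RA"), a benchmark ("an effectiveness of RZV in preventing HZ of 85"%), and, under Figure 6, "2:1 matching of comparators to RZV exposed patients". It reports two thresholds:

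- "for 2,000 RZV-exposed person-years, the upper 95% confidence interval bound of vaccine effectiveness would exclude 85"% when the point estimate is 66.7% or lower.
- At 4,000 exposed PY, the same holds at 70.8% or lower.

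It ties these sizes to the feasibility counts in Table 1. That table shows 1,932 two-dose recipients with a tofacitinib dispensing, RA and UC together.

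The analysis sections are organised differently. Section 9.7.3.1 states: "All analyses will be performed separately within the UC and RA cohorts". Sections 9.1 and 9.7.3.2 repeat this, and Sections 9.7.1 and 9.7.2 give each disease its own propensity models and weights. Section 9.7.3.1 then narrows the target: two-dose recipients who are "current users of tofacitinib at the time of receipt of both doses will be the main comparison". The only pooling mentioned, in Section 9.4, joins the two databases, not the two diseases.

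**The concern.** The precision statement and the analysis plan refer to different populations. In any given scenario each disease cohort holds only part of the pooled person-years, and the both-doses subgroup holds less again. A reader of Section 9.5 would expect the primary results to separate VE in the mid-60s from the 85% benchmark. The disease-specific estimates, UC above all, may be unable to do so. A wide UC interval that includes 85% could then be misread as preserved effectiveness, when it only reflects few events. Pooling decided after a sparse UC result would look data-driven.

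**Working it through.** **Inputs.** From Section 9.5: comparator HZ rate 0.012 per PY, 2:1 comparators, benchmark VE 85%, 95% interval, totals of 2,000 and 4,000 exposed PY. Assumed: the RA:UC split of vaccinees, which the protocol does not give. All RA and UC patients in Table 1 suggest 446,618 / (446,618 + 202,619) = 68.8% RA, so 69:31 is used first and then varied.

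**Formulas.** With PY exposed person-years:

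- Expected comparator events b = 0.012 × 2 × PY, rounded.
- With *a* vaccinee events, VE = 1 − 2a/b.
- Exact: the lower rate-ratio limit is 2p/(1 − p), where p is the 2.5% Clopper-Pearson limit for *a* out of a + b. Mid-P uses the mid-P version of p.
- Wald: the lower rate-ratio limit is (2a/b) × exp(−1.96 × √(1/a + 1/b)).
- Upper VE bound = 1 − lower rate-ratio limit. The threshold is the VE at the smallest *a* whose upper bound is below 85%.

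**Step 1: reproduce the plan's figures.**

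- 2,000 PY: b = 48. With 8 events, VE = 1 − 16/48 = 66.7%. The upper bound is 84.2% by Wald, 85.3% by mid-P and 86.4% exact, so only Wald excludes 85%. Exact and mid-P need 9 events, VE 62.5% (bounds 83.8% and 82.6%).
- 4,000 PY: b = 96. With 14 events, VE = 1 − 28/96 = 70.8%. The upper bound is 84.6% exact and 83.9% mid-P. With 13 events (72.9%) these become 86.1% and 85.4%, so 70.8% is their threshold. Wald already excludes 85% at 13 events (84.8%), so its threshold is 72.9%.
- The effect sizes follow: (85 − 66.7)/85 = 21.5% and (85 − 70.8)/85 = 16.7%.

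No single one of these three methods gives both stated thresholds.

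**Step 2: are 2,000 and 4,000 pooled totals?** 2,000/1,932 = 1.04 and 4,000/1,932 = 2.07 PY per two-dose recipient. These are plausible mean follow-up times, which fits a pooled reading.

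**Step 3: split 69:31 by disease, same method throughout.** Entries are threshold VE (vaccinee vs comparator events).

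| Cohort | PY | Exact | Mid-P | Wald |
|---|---|---|---|---|
| Pooled | 2,000 | 62.5% (9 vs 48) | 62.5% (9 vs 48) | 66.7% (8 vs 48) |
| RA | 1,376 | 57.6% (7 vs 33) | 57.6% (7 vs 33) | 63.6% (6 vs 33) |
| UC | 624 | 33.3% (5 vs 15) | 46.7% (4 vs 15) | 46.7% (4 vs 15) |
| Pooled | 4,000 | 70.8% (14 vs 96) | 70.8% (14 vs 96) | 72.9% (13 vs 96) |
| RA | 2,752 | 66.7% (11 vs 66) | 66.7% (11 vs 66) | 69.7% (10 vs 66) |
| UC | 1,248 | 53.3% (7 vs 30) | 60.0% (6 vs 30) | 60.0% (6 vs 30) |

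**Step 4: vary the split, 2,000 PY in total.**

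- 80:20: RA (1,600 PY) 57.9% exact, 63.2% mid-P or Wald; UC (400 PY) 20.0% exact or mid-P, 40.0% Wald.
- 50:50: each (1,000 PY) 50.0% exact or mid-P, 58.3% Wald.

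In every case the disease-specific threshold is below the pooled one by the same method.

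**Step 5: what the counts omit.** Table 1 does not apply current tofacitinib use at the second dose, 365 days of enrolment, or use at both doses. In Table 2, (544 + 1,069)/(649 + 1,248) = 1,613/1,897 = 85% of tofacitinib-and-Shingrix patients had at least one year of prior enrolment. The protocol gives no count for the both-doses group.

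**The case against.** - **Precision is indexed to person-years.** This stands. Any cohort with 2,000 exposed PY has the 2,000-PY precision, whichever disease it is. At 69:31, RA alone would need about 1.5 PY per patient if all 1,932 recipients qualified (2,000 / (0.688 × 1,932)). Figure 6 is not available here and may show smaller sizes. A reader might infer that no planned estimate can ever reach the stated precision; the protocol does not support that. The figures fail to match only when read as pooled totals.
- **The RA loss can be overstated.** This stands. Setting an exact RA threshold of 57.6% against the stated 66.7% suggests a drop of 9.1 points, but it mixes methods. Like for like, the drop is 4.9 points (exact or mid-P) or 3.1 (Wald).
- **The comparator rate may be too low.** This stands in part. The 1.2 per 100 PY is for patients not on tofacitinib, whereas the comparators are tofacitinib users, and Section 7 reports higher HZ rates on tofacitinib than on placebo. At an assumed 2.4 per 100 PY, the exact thresholds at 69:31 of 2,000 PY rise to 66.7% in RA and 53.3% in UC. The pooled threshold rises too, to 70.8%, so the gap remains.
- **The protocol already hedges.** Section 9.5 calls the counts informational, Section 9.1 makes the both-doses comparison depend on sample size, and Section 9.9 warns that user numbers may diverge. None of these addresses splitting by disease.
- **Validity is untouched.** This stands. The data are a fixed claims extraction, and the precision text changes neither the estimator nor its bias.

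**Conclusion.** The mismatch is real and lies within the current protocol: Section 9.5 describes a combined RA-or-UC estimate, and Sections 9.1 and 9.7.3 never produce one. At an assumed 69:31 split the effect is modest for RA (57.6% against 62.5%, or 63.6% against 66.7% by Wald, at 2,000 PY). It is large for UC (33.3% or 46.7%, against 62.5% to 66.7%). At 4,000 PY the exact or mid-P threshold of 70.8% becomes 66.7% in RA and 53.3% or 60.0% in UC.

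These sizes rest on the assumed split, the protocol's 1.2 per 100 PY, whole expected events, and unweighted, independent observations. Weighting, repeat sampling of comparators and the both-doses restriction would probably reduce precision further; a higher comparator rate would improve it. A reader might also infer that the separate-by-disease design is itself wrong and that the primary estimate must be pooled. The protocol does not support this: separate cohorts, models and weights are a consistent design choice, and pooling would assume a common effect.

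**What to change.** Restate Section 9.5 separately for UC and for RA, and within each for the both-doses main comparison:

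1. Give exposed counts and expected person-years by disease after applying the eligibility criteria (current use at the second dose, 365 days of enrolment, use at both doses).
2. Name one interval method and use it for every row. The current 66.7% and 70.8% do not both come from any one of the exact, mid-P and Wald methods.
3. State the resulting thresholds, including the less favourable UC figures.

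A disease-stratified pooled HZ estimate with a disease interaction may be prespecified as a supplementary analysis, without replacing the separate primary analyses. The limit of "Up to 2 comparators for each RZV initiator will be selected" can stay as it is: a cap of five would cut the standard error of the HZ log hazard ratio by only about 4%.

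The cost is a feasibility query, revised wording in one section and, if the supplement is adopted, one extra model. It should be done before results are known.

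### Section 9.5 presents the largest observed effectiveness that still excludes 85% as if it were a true loss; at that true loss the study would exclude 85% only about half the time

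*Protocol*

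**What the plan says.** Section 9.5 (Study Size) of the protocol sets out to calculate "the sample size necessary to exclude 85% from the 95% confidence interval for the RZV effectiveness estimate" in tofacitinib users. Its inputs are these:

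- Rate: "Assuming a background rate of HZ of 1.2 cases per 100 person-years among non-tofacitinib exposed patients with UC and RA".
- Reference value: "an effectiveness of RZV in preventing HZ of 85" per cent.
- Allocation, from the note under Figure 6: "Assumptions: 1.2% HZ rate in unexposed; 2:1 matching of comparators to RZV exposed patients".

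The result is first given as a condition on the estimate: "for 2,000 RZV-exposed person-years, the upper 95% confidence interval bound of vaccine effectiveness would exclude 85% if the point estimate" in tofacitinib-exposed patients "were 66.7% or lower". The parenthesis that follows changes the subject from the estimate to the drug's effect: "corresponding to an effect size of 21.5%, meaning that tofacitinib reduces the RZV effectiveness by 21.5" per cent. The sentence for 4,000 person-years has the same form, with 70.8% as the threshold and "corresponding to an effect size of 16.7%, meaning that tofacitinib reduces the RZV effectiveness by 16.7" per cent as the reading. The section gives no power, and no true effect that would be detected with a stated probability.

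**The concern.** A point estimate that just meets a criterion and a true effect that would reliably meet it are different quantities. If the true effect sits at the threshold, the estimate falls on either side of it about equally often, so the criterion is met roughly half the time. The parentheses move from the first quantity to the second.

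Section 9.5 is the protocol's only account of what a study of this size can show, and the study is a post-marketing commitment. A reader could reasonably take 21.5% and 16.7% as the losses of effectiveness that 2,000 and 4,000 person-years can demonstrate. The losses that can be shown with good probability are larger.

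**Working it through.** **Inputs (all from section 9.5).** Comparator rate 0.012 per person-year. Reference VE 85%, that is, a rate ratio of 0.15. Two-sided 95% interval. Comparator person-years are twice the RZV person-years.

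**1. Reproducing the stated thresholds.** Expected comparator events are 0.012 × 2 × 2,000 = 48 and 0.012 × 2 × 4,000 = 96. With *a* vaccinated and *b* comparator events, VE = 1 − 2*a*/*b*.

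- 8 against 48: VE = 1 − 16/48 = 66.7%. The upper limit is 84.2% (Wald on the log rate ratio), 85.0% (Jeffreys, 0.8496), 85.3% (mid-P) or 86.4% (exact conditional).
- 14 against 96: VE = 1 − 28/96 = 70.8%. The upper limit is 83.4% (Wald), 83.8% (Jeffreys), 83.9% (mid-P) or 84.6% (exact). One event fewer (13 against 96) gives 85.3% by Jeffreys.

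Both thresholds are therefore recovered. Among the methods tried, only Jeffreys yields both; the others yield one or the other.

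**2. Reproducing the stated effect sizes.** 1 − 66.7/85 = 21.5% and 1 − 70.8/85 = 16.7%. Both are correct as arithmetic.

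**3. Chance of excluding 85% when the true VE equals the threshold.** Treat the two counts as independent Poisson variables with means 0.012 × (1 − VE) × PY (vaccinated) and 0.012 × 2 × PY (comparator). The probability wanted is the sum, over all pairs of counts, of the probability of each pair for which the lower limit of the rate ratio exceeds 0.15. The vaccinated means are 0.012 × 0.333 × 2,000 = 8.0 and 0.012 × 0.292 × 4,000 = 14.0.

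| Rule for excluding 85% | 2,000 PY, true VE 66.7% | 4,000 PY, true VE 70.8% |
|---|---|---|
| Protocol's threshold applied to the estimate | 49% | 48-49% |
| Exact conditional | 41% | 51% |
| Mid-P | 47% | 56% |
| Jeffreys | 48% | 57% |
| Wald | 52% | 60% |

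**4. True VE giving an 80% chance.** The same sum is solved for VE; the relative reduction is (85 − VE)/85.

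| Rule | 2,000 PY: true VE (reduction) | 4,000 PY: true VE (reduction) |
|---|---|---|
| Protocol's threshold | 54.6% (36%) | 62.9% (26%) |
| Exact conditional | 51.9% (39%) | 63.7% (25%) |
| Mid-P | 54.1% (36%) | 64.8% (24%) |
| Wald | 55.9% (34%) | 65.8% (23%) |

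**5. The same question in person-years.** With mid-P limits, an 80% chance at a true VE of 66.7% needs about 4,750 RZV-exposed person-years, against the 2,000 quoted. At a true VE of 70.8% it needs about 7,500, against 4,000.

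**The case against.** The strongest reply is that nothing has been miscalculated. The sentence is conditional on the point estimate, no power is claimed, and sizing an observational study by the precision of its interval is legitimate. All of that stands. It does not rescue the parentheses, which do not describe an estimate: they say what tofacitinib does to effectiveness.

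A second reply is that the probabilities depend on the assumed 1.2 per 100 person-years. That rate is given for patients not exposed to tofacitinib, and section 7 reports more herpes zoster on tofacitinib. This also stands. Purely as an assumption, with true VE 66.7% and 2,000 person-years, a comparator rate of 2.0 per 100 would give 62-71% and a rate of 3.0 would give 79-84%. At a higher rate, however, 66.7% would no longer be the threshold either, so the restated figures should be tied to the protocol's rate.

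A third reply is that nothing in the analysis hangs on this. Section 9.7 has no decision rule at 85%, and the study uses existing data with no fixed target. That is true, and it is why this is a correction to a statement rather than to the design.

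A reader might go further and infer that the plan treats failure to exclude 85% as evidence that effectiveness is preserved, or is at fault for giving no lower limit. The documents do not support that. The objectives are to estimate and compare rates, section 9.7.3 reports hazard ratios with 95% intervals, so both limits will be seen, and no sentence equates non-exclusion with no loss. Nor would such intervals be empty: with 7 against 96 events (VE 85.4%), the exact interval is 68.8% to 94.3%.

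**Conclusion.** The point holds as a mislabelled quantity. The values 66.7% and 70.8% are correctly derived as critical estimates; reading them as true reductions of 21.5% and 16.7% is wrong. At those true reductions 85% is excluded 41-52% of the time at 2,000 person-years and 48-60% at 4,000. The reductions detectable with 80% probability are 34-39% and 23-26%, about 1.6 to 1.8 times the stated figure at the smaller size (34/21.5 to 39/21.5) and 1.4 to 1.6 times at the larger (23/16.7 to 26/16.7).

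These results rest on the protocol's 1.2 per 100 person-years, 2:1 person-time, and independent Poisson counts without weighting or repeated sampling. The ranges reflect the choice of interval method, which the text of section 9.5 does not name. The conclusion is the same under every method tried.

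**What to change.** In section 9.5:

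- Describe 66.7% and 70.8% as the largest observed estimates whose interval excludes 85%.
- Delete or reword the two parentheses so that they no longer state what tofacitinib does to effectiveness.
- Add, for each size, the true VE and relative reduction giving an 80% probability of excluding 85%, naming the interval method and stating that the figures are conditional on 1.2 per 100 person-years.

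The expected interval when true VE is 85% could be added as a help to the reader, but its absence is not an error.

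The cost is a few sentences and one short calculation. Study size, cohorts and analysis stay as they are. The only downside is that the stated reduction becomes less favourable.
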